10.0 Statistical Considerations

Given the project focus on testing indirect (mediated) effects of the aerobic exercise manipulation via EO enhancement (mediator) on CP intensity (Aim 1), morphine analgesic requirements (Aim 2), and associated abuse relevant subjective effects (Aim 3), the project is powered specifically for the proposed bias-corrected bootstrap mediation analyses. Empirical power estimates for this mediation analysis approach are available⁶⁴. The mediation analyses will test the mediation model presented in Figure 2 below. The power estimates below jointly take into consideration the effect sizes for the a and b paths in Figure 2. The effects of exercise on EO analgesia (a path) can be derived from 3 studies in healthy individuals reporting differences in pain sensitivity following acute exercise between placebo and EO blockade (naloxone) conditions^{55,68,74}.

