Effect sizes ranged from $d=.6$ to $d=1.2$ in directions indicating that opioid blockade reduced post-exercise analgesia, suggesting that EO function partly mediated the effect of acute exercise on pain intensity. The mean effect size across these studies for the impact of EO mechanisms on exercise-related analgesia was $d= .93$ (equivalent to $r=0.42$). This effect size is key to initial analyses of Specific Aim 1. The proposed sample size will result in a power exceeding 0.90 for testing effects of the exercise manipulation on EO function (two-sided $p<.05$ significance criterion). Effect size estimates for the b path in the mediational model reflecting influences of EO function on morphine responses can be derived from our prior work, which indicated an average effect size of $r=0.27$ for associations between natural variations in EO function (opioid blockade effects) and analgesic responses to a single morphine dose across all pain measures and both laboratory evoked pain tasks¹⁸. Effect size for the b path reflecting influences of EO function on chronic back pain intensity can be estimated from Bruehl et al.²⁵, with an effect size of $r=0.26$ for associations between EO analgesic function in the laboratory and diary ratings of chronic back pain intensity (greater EO function was associated with lower daily back pain intensity). Given these effect sizes for the a and b paths in the mediation model, the total sample size for the proposed project was selected as $n=116$, resulting in a power of 0.80 (two-tailed $p<.05$ criterion for significance) for testing mediation effects hypothesized in Aims 1-3 using the proposed bootstrap approach (based on Fritz and MacKinnon⁶⁴).

Data Reduction and Analyses

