post-manipulation) to determine whether EO function increased in the aerobic exercise condition only. We will then test whether group differences in pre- to post-manipulation EO changes mediate group differences in pre- to post-manipulation reductions in evoked pain responsiveness and CP intensity using the bias-corrected bootstrap mediation testing approach of Preacher and Hayes¹⁰⁰. This approach is statistically powerful and not dependent on any assumptions about the sampling distribution of the variables, and was used successfully in our recently published work¹⁸. Per Preacher & Hayes¹⁰⁰, the only precondition for testing mediation will be presence of an effect to be mediated (i.e., the exercise condition is associated with significantly greater reductions in evoked pain responses and CP intensity than the control condition). For any outcomes for which this precondition is met, bootstrap tests of mediation will proceed using the Indirect procedure for SPSS^{100, 101} (<http://www.afhayes.com/spss-sas-and-mplus-macros-and-code.html#sobel>) as in our recent work¹⁸. If the 95% CI for the indirect effect in a given model does not include zero, this will indicate that the hypothesized indirect (mediated) effect is significant at $p < .05$. In this case, a significant indirect path will indicate that the link between aerobic exercise condition and reduced evoked pain responsiveness or CP intensity is significantly mediated by exercise-related EO enhancements. Significant direct and indirect paths jointly for the same outcome will indicate partial mediation. A significant direct path in the absence of a significant indirect path will be interpreted as indicating that the effects of the exercise manipulation on that outcome are mediated via non-opioid mechanisms.

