Aim 2: To determine whether the exercise manipulation is related to achieving analgesic targets at lower opioid analgesic dosages, and whether these changes in analgesic requirements are mediated by pre-post EO changes. We will calculate dose response curves (per Prentice¹⁰²) based on morphine condition evoked pain responses at the four incremental morphine dose levels (separately for pre- and post-manipulation). Based on results of our prior work¹⁸, a 25% reduction in pain sensitivity relative to pre-exercise placebo pain responses will be the target. The total dosage of morphine needed at pre-manipulation BL to achieve a 25% reduction in pain responses (based on the dose response curve) will be compared to the dose of morphine needed to achieve a 25% pain reduction at post-exercise. We will conduct Group (exercise, control) x Time (BL, post-manipulation) mixed design ANOVAs to determine whether the total morphine dose required to achieve 25% pain relief decreased significantly in the exercise group only. We will then use mediation analysis procedures as described above to test whether group differences in pre- to post-manipulation EO changes mediate group differences in pre- to post-manipulation reductions in morphine dosage required to achieve 25% relief. The only precondition for conducting these mediation tests will be that there is an effect to be mediated, i.e., the exercise manipulation significantly alters the morphine dosage required to achieve 25% pain relief.

Aim 3: To determine whether the exercise manipulation is related to achieving a 25% morphine-induced reduction in evoked pain responsiveness with fewer negative side effects and abuse-relevant effects, and whether these changes are mediated by pre- to post-manipulation EO changes. Aim 3 analyses will parallel Aim 2 except that side effects and abuse-relevant effects at the 25% pain reduction target will be the DV.

Secondary Analyses.

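### The stated 0.80 mediation power leaves out the chance of passing the plan's own precondition, a significant exercise effect on the outcome, and the plan gives no figure from which that chance could be worked out

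*Combined protocol and SAP*

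**What the plan says.** Section 10.0 (Statistical Considerations) powers the project for bias-corrected bootstrap mediation tests and names the inputs: "The power estimates below jointly take into consideration the effect sizes for the a and b paths in Figure 2". The a path (exercise to EO function) is d=0.93, r=0.42. The b path (EO function to outcome) is r=0.27 for morphine analgesic response and r=0.26 for diary back pain. The total sample of 116 is described as "resulting in a power of 0.80" at two-sided 0.05, "for testing mediation effects hypothesized in Aims 1-3 using the proposed bootstrap approach". The only other power figure, above 0.90, is for exercise on EO function, which is the a path again.

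The Primary Analyses in the same section add a first step. For Aim 1, "the only precondition for testing mediation will be presence of an effect to be mediated", which the plan explains as a significantly greater reduction under exercise than under control. The rule works outcome by outcome: "For any outcomes for which this precondition is met, bootstrap tests of mediation will proceed". Aim 2 repeats it for required morphine dose: "The only precondition for conducting these mediation tests will be that there is an effect to be mediated". For side effects and abuse-relevant effects, "Aim 3 analyses will parallel Aim 2".

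The plan allows for a direct effect of exercise outside the EO path: "Significant direct and indirect paths jointly for the same outcome will indicate partial mediation". It gives no size for that direct effect (c'), for the total exercise effect on any outcome, or for the power of the first step.

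**The concern.** The power statement covers one test, and the plan requires two significant results. The bootstrap test depends mainly on a and b. The precondition depends on the total effect, a x b + c'. A product of two moderate paths is small, so an indirect effect can be detectable while the total effect is not.

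A reader will take 0.80 as the chance that a true EO pathway is confirmed. If the precondition often fails, mediation will often go untested, and the absence of a mediation result could be misread as evidence against the EO hypothesis on which the project rests.

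**Working it through.** **Inputs.** From section 10.0: n=116, two-sided 0.05, a=0.42, b=0.26 (diary pain) or 0.27 (morphine response). From section 7.0: half are assigned to exercise, taken as 58 + 58. Assumed because the plan is silent: the value of c', what kind of quantity the quoted b is, and all 116 analysed.

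**1. Reproduce the plan's figures.**
- r = d/√(d² + 4) = 0.93/√(0.8649 + 4) = 0.42, as stated.
- Simulation with group coded ±1, M = aX + e, Y = bM + c'X + e, M and Y with unit variance, c'=0, bias-corrected 95% bootstrap interval, 6,000 trials: power of the indirect-effect test is 0.774 (b=0.26) and 0.803 (b=0.27). The stated 0.80 reproduces for this test run unconditionally.

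**2. Power of the precondition when the EO path is the only path (c'=0).**
- Total r = a x b = 0.42 x 0.26 = 0.109, or 0.42 x 0.27 = 0.113. With d = 2r/√(1 − r²), that is d of about 0.22 to 0.23.
- Fisher z for r=0.1092: atanh(0.1092) x √113 = 0.1096 x 10.63 = 1.166. Power = Φ(1.166 − 1.96) + Φ(−1.166 − 1.96) = 0.214. For r=0.1134 it is 0.228. Simulation gives 0.208 and 0.220.
- For 80% power at this step alone, total r must be tanh((1.96 + 0.8416)/√113) = 0.26, or d about 0.52.

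**3. Joint power at c'=0** (precondition met and bootstrap interval excludes zero).
- Simulated: 0.162 (b=0.26) and 0.178 (b=0.27).
- Trials with a significant indirect effect that the plan would not test: 0.774 − 0.162 = 0.61, and 0.803 − 0.178 = 0.63.
- Power once the precondition is met: 0.162/0.208 = 0.78, and 0.178/0.220 = 0.81.

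**4. Joint power with a direct effect** (b=0.26 / 0.27; 1,500 trials per cell for c' other than 0, standard error at most √(0.25/1500) = 0.013).

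| Reading of the quoted b | c'=0 | c'=0.10 | c'=0.20 | c'=0.26 |
|---|---|---|---|---|
| Coefficient given group, outcome variance fixed at 1 | 0.16 / 0.18 | 0.49 / 0.53 | 0.77 / 0.80 | 0.82 / 0.85 |
| Coefficient given group, residual variance fixed | 0.16 / 0.18 | 0.47 / 0.51 | 0.71 / 0.73 | 0.76 / 0.78 |
| Zero-order correlation (b = r − a x c') | 0.16 / 0.18 | 0.34 / 0.38 | 0.41 / 0.44 | not run |

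On the zero-order reading, joint power falls back to 0.35 / 0.38 at c'=0.30. If the quoted r is instead a partial correlation, joint power is 0.21 to 0.23 at c'=0 and, for b=0.26, 0.54 at 0.10 and 0.82 at 0.20. A direct effect opposing the EO path (c'=−0.05, residual variance fixed) gives 0.07 / 0.08.

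**5. Which outcomes have a b path.** Section 10.0 gives one for diary back pain and one for morphine analgesic response. It gives none for the Aim 3 side-effect and abuse-relevant outcomes, although the 0.80 is claimed for Aims 1-3.

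**The case against.** The strongest reply is that 0.80 is not wrong. It reproduces, the plan says openly that only a and b enter it, and when b is a coefficient given group it is also roughly the power of the bootstrap test once the precondition is met (0.78 and 0.81 in step 3). That stands. A reader might infer that the figure is an arithmetic error or describes a test the trial never runs. The documents support neither. What is missing is the chance of reaching the test.

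A second reply is that exercise probably has a direct effect, so the loss may be small. The Background cites trials in which exercise reduces chronic pain, and the plan foresees partial mediation, so c'=0 need not be the expected case. But the plan sizes no such effect, and on the zero-order reading even a sizeable one does not bring joint power much past 0.45.

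Third, evoked pain. A reader might say that its missing b path undermines the 0.80 as well. This is weak: hypothesis 1b and the opening of section 10.0 name only chronic pain intensity for Aim 1 mediation, so power for evoked pain was arguably never claimed, although the Aim 1 analysis does test it. The gap for Aim 3 is clear.

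Fourth, the precondition limits false positives. With b=0 and c'=0, dropping it would raise the false-positive rate per outcome from 0.3% to 7.9% with the bias-corrected interval. That is a good reason to keep it.

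**Conclusion.** The point holds in a limited form. The 0.80 is power for the indirect-effect test and is not shown for the two-step procedure in the Primary Analyses. With no direct effect, the plan's own inputs give a total effect of r about 0.11, a precondition met about 0.21 to 0.24 of the time, and joint power of about 0.16 to 0.20 (slightly higher if the quoted b values are partial correlations). With a same-direction direct effect and b taken as a coefficient given group, joint power is about 0.5 at c'=0.10 and 0.7 to 0.8 at c'=0.20.

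A reader might infer that the trial has 16% power for mediation, or that power lies between 0.16 and something above 0.80. Neither follows. An opposing direct effect goes lower. Exceeding 0.80 depends on how b and the variances are defined: with residual variance fixed, joint power cannot exceed the unconditional 0.77 to 0.80. Nor does the total effect alone fix joint power: at total r=0.25 it runs from 0.17 (b=0.10) to 0.79 (full mediation). All figures assume 116 analysed. The firm conclusion is that the documents do not let a reader judge the chance of confirming mediation.

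**What to change.** Keep the precondition and restate the power paragraph in section 10.0:

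1. Say that 0.80 is the power of the bootstrap indirect-effect test itself and does not include the chance of meeting the precondition.
2. For each outcome, state the expected total exercise effect, the power of the precondition and the resulting joint power. Give the assumptions: whether b is a coefficient given group or a zero-order correlation, the size and direction of c', the variance convention, and the number analysed.
3. Limit the 0.80 claim to chronic pain intensity and morphine response, or state a b path for the Aim 3 side-effect and abuse-relevant outcomes, and for evoked pain if power is claimed for it.

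The illustrative table above should not be pasted into the protocol; the team needs figures built on its own stated assumptions.

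Optionally, report the indirect effect with a bootstrap interval for every prespecified outcome as a supplementary analysis, whether or not the precondition is met, and describe it as an indirect effect rather than as the explanation of a demonstrated benefit.

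The cost is some text and a short power calculation. No patients, visits or decision rules change. The stated power may fall below 0.80, and the team would have to accept or justify that openly.

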The other study drug, morphine, is an FDA-approved opioid analgesic with a very long history of use in standard clinical practice. It can produce dose-dependent side effects including sedation, somnolence, nausea, brief vomiting, euphoria, and respiratory depression. The cumulative dose to be used in the proposed study (0.09 mg/kg) will be weight adjusted, and represents a relatively low dose within the normal range of dosages used in standard clinical practice, representing a dosage only slightly larger than in our recent work (0.08 mg/kg; Bruehl et al., 2013). This should help limit any negative side effects. The half-life of morphine is approximately 2 hours, and study participants will be kept under observation in each study session until any side effects remit to the point where it is safe for them to leave unassisted. If morphine side effects are severe, these effects will be immediately reversed by administration of naloxone as determined appropriate by the study physician.

As part of this study, half of the participants will be randomly assigned to undergo a 6-week supervised aerobic exercise manipulation as described above. To maximize safety with this type of exercise, individuals with a history of cardiovascular disease are excluded from participating in this study. The intensity of this aerobic exercise training will start low but progressively increase over the 6-week intervention period. Safety and possible discomfort associated with these increases in exercise intensity will be minimized via close monitoring by a certified personal trainer of participant's heart rate, perceived exertion levels, and back pain intensity during exercise. Exercise intensity will be adjusted as appropriate to maximize the participant's level of conditioning while minimizing exacerbation of back pain. In addition, participants will be able to choose your preferred form of exercise from several available options.

In the event new information becomes available that may affect the risks or benefits associated with this study, participants will be notified so that they can make an informed decision whether or not to continue their participation in this study. There may be unknown or unanticipated adverse effects in addition to those listed.

8.0 Reporting of Adverse Events or Unanticipated Problems Involving Risk to Participants or Others

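### The bias-corrected bootstrap interval labelled p<.05 rejects up to about 7–8% of the time at n=116 when exactly one mediation path is zero

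*Combined protocol and SAP*

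**What the plan says.** All of this is in Section 10.0 of the combined protocol and SAP, unless noted.

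- Sample size: "the project is powered specifically for the proposed bias-corrected bootstrap mediation analyses". With n=116 the plan reports "resulting in a power of 0.80 (two-tailed $p<.05$ criterion for significance) for testing mediation effects hypothesized in Aims 1-3".
- Method, under Primary Analyses, Aim 1: mediation is tested "using the bias-corrected bootstrap mediation testing approach". The same procedure carries over to Aims 2 and 3.
- Decision rule: when the bootstrap 95% interval leaves out zero, "this will indicate that the hypothesized indirect (mediated) effect is significant at" the .05 level.
- Precondition: the mediation test is run only for outcomes on which exercise differs significantly from control.
- Reading of the results: a significant direct path without a significant indirect path is to be taken as a non-opioid mechanism.
- Allocation (Section 7.0 Risks): "half of the participants will be randomly assigned to undergo a 6-week supervised aerobic exercise manipulation".

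The plan does not examine the type I error of this interval. It plans no percentile interval, joint-significance test or other sensitivity analysis for the indirect effect.

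**The concern.** The indirect effect is the product of the a path (exercise to EO function) and the b path (EO function to outcome, given group). It is zero when either path is zero. When one path is real and the other is zero, the bias correction shifts the interval's end points so that it excludes zero too often. The p<.05 label then promises a level that the method lacks.

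The case that matters most is the one the trial is meant to resolve: exercise raises EO function and also relieves pain, but EO function is not the reason. A false positive there reports an opioid mechanism where the plan's own rules should point to a non-opioid one. The same liberality also supplies part of the 0.80 power on which n=116 was chosen.

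**Working it through.** **Inputs from Section 10.0 and Section 7.0:** n=116, split 58/58; a path d=0.93 (r=0.42), range d=0.6 to 1.2; b path r=0.27 (morphine response) and r=0.26 (chronic pain); two-sided 0.05.

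**Assumptions not in the documents:** normal errors, complete data, one mediator, no covariates, 1,000 resamples (5,000 in a check), and any direct effect c'.

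**Model:** M = aX + error; Y = c'X + bM + error; indirect effect = ab. Cases are resampled.

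- Bias-corrected interval: z0 is the normal quantile of the share of bootstrap products below the estimate. The limits are the bootstrap quantiles at Φ(2·z0 ± 1.96).
- Percentile interval: the 2.5% and 97.5% bootstrap quantiles.
- Joint significance: a and b each p<.05.

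**Step 1: reproduce the plan's figures.**

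- r = d/√(d²+4) = 0.93/√4.865 = 0.42, as stated.
- a-path power: 0.93·√(58/2) = 5.01; Φ(5.01 − 1.96) ≈ 0.999. The plan says above 0.90.
- Mediation power, with r read as a standardised path (10,000 trials):

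| b | Bias-corrected | Percentile | Joint significance |
|---|---|---|---|
| 0.27 | 0.808 | 0.773 | 0.767 |
| 0.26 | 0.778 | 0.736 | 0.732 |

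The stated 0.80 reproduces at b=0.27 and falls slightly short at 0.26. Other readings of r give bias-corrected power of 0.82–0.83 (coefficients with unit residual variance) or 0.85–0.86 (partial correlations). A separate 4,000-trial run gave 0.78 for the percentile interval at b=0.27.

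**Step 2: false-positive rate without the precondition** (8,000 trials, c'=0). Standard error near 7%: √(0.07·0.93/8000) = 0.3 points.

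| True paths | Bias-corrected | Percentile | Joint significance |
|---|---|---|---|
| d=0.6, b=0 | 8.0% | 4.8% | 4.6% |
| d=0.93, b=0 | 7.8% | 6.0% | 5.1% |
| d=1.2, b=0 | 7.5% | 6.5% | 5.2% |
| a=0, b=0.27 | 7.3% | 4.0% | 4.2% |
| d=0.3, b=0 (weak) | 3.6% | 1.6% | 1.7% |
| a=0, b=0.14 (weak) | 3.1% | 1.1% | 1.4% |
| both zero | 0.7% | 0.2% | 0.3% |

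With 5,000 resamples (4,000 trials), the rates were 8.7%, 6.4% and 5.9% at d=0.93, b=0, and 7.1%, 4.2% and 4.4% at a=0, b=0.27. Other repeat runs at these two settings gave bias-corrected rates of 6.6% to 8.1%.

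**Step 3: add the precondition and an assumed direct effect.** An effect of 0.53 SD is one that 58 per arm detects about 80% of the time.

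| True state | Precondition met | Bias-corrected, among tests run | Percentile, among tests run | Bias-corrected, all trials |
|---|---|---|---|---|
| d=0.93, b=0, c'=0 | 4.9% | 6.9% | 5.1% | 0.3% |
| d=0.93, b=0, c'=0.53 | 80.2% | 7.5% | 5.8% | 6.0% |
| d=0.93, b=0, c'=0.8 | 99.1% | 7.8% | 6.1% | 7.8% |
| d=0.6, b=0, c'=0.53 | 80.8% | 8.1% | 5.0% | 6.6% |
| a=0, b=0.27, c'=0 | 5.1% | 12.3% | 8.3% | 0.6% |
| a=0, b=0.27, c'=0.53 | 81.2% | 6.7% | 3.5% | 5.4% |

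A smaller run (2,500 trials; d=0.93, b=0) put the all-trials rate at 3.3% for c'=0.3 and 4.9% for c'=0.4.

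**The case against.** The strongest case on the other side has five parts.

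1. **The rate is not constant.** A reader might infer a flat 7–8% at n=116. The second table rules that out: it is under 1% with both paths zero and about 3–4% when the only real path is weak. This stands.
2. **The precondition limits how often a false claim is made.** A reader might infer that the trial would wrongly announce EO mediation about one and a half times as often as stated. The plan runs the test only after a significant group effect. With no direct effect, only 0.3–0.6% of trials at the plan's path sizes both meet the precondition and reject. The all-trials rate passes 5% only above a direct effect of about 0.4 SD, and the documents give no such figure. This stands as a limit on frequency. It does not repair the interval: once a non-opioid effect lets the test be run, the error rate is as high as without the precondition.
3. **The percentile interval does not hit 5% either.** It gives 6.0–6.4% at d=0.93, b=0, and joint significance comes closest (5.1–5.9%). This stands, and the fix should not be described as restoring the level exactly.
4. **The sample size was built for the bias-corrected test.** Changing the interval takes power below 0.80. This is a real cost. But 3.5 points (0.808 − 0.773) to 4.2 points (0.778 − 0.736) of the stated power come with the excess rejections.
5. **Not everything in the three aims depends on this test.** A reader might infer that it does. Part (a) of each aim (Section 2.0) is tested by Group x Time ANOVA; only the part (b) hypotheses use the bootstrap.

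The rates are also two-sided. About half of the false rejections lie in the hypothesised direction (4.1% at d=0.93, b=0, against a nominal 2.5%).

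**Conclusion.** The concern holds in a limited form. At n=116 and the plan's path sizes, the bias-corrected rule rejects up to about 7–8% of the time against a stated 5% when exactly one path is zero. The excess of 2–3 points is small but far outside simulation error. It persists among the tests run when exercise relieves pain by a non-opioid route, which is the distinction the mediation analysis is meant to draw.

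The documents do not support a constant inflated rate, an inflated overall claim rate in every scenario, or the view that all results of the three aims are affected. If exercise has no non-opioid effect, the overall false-claim rate is well under 5%.

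The conclusion rests on normal errors, complete data on all 116, a single mediator without covariates, 1,000–5,000 resamples and, for the result after the precondition, an assumed direct effect of about 0.5–0.8 SD. Multiplicity across outcomes is not counted.

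**What to change.** - Make the percentile bootstrap 95% interval primary for the part (b) mediation hypotheses of Aims 1–3. This lowers the rate to about 5–6% in the case of most concern.
- Report the bias-corrected interval as supplementary, without calling it a 5% test. Add a joint-significance test of the a and b paths as a check.
- Restate mediation power at n=116, before the precondition is applied, as about 0.77–0.78 for b=0.27 and about 0.74 for b=0.26. Say that r is read as a standardised path, with normal errors and complete data.

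The work is one analysis option and a short edit to Section 10.0; design and data collection do not change. The price is 3–4 points of stated power, which puts it below the 0.80 target, and the plan should say so.

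For scale, 0.80 power by joint significance needs about ((1.96 + 0.84)/atanh(ρ))² + 4 evaluable participants. Here ρ is the partial correlation for b, equal to b√(1 − 0.42²)/√(1 − (0.42b)²). That gives ρ=0.247 and about 128 participants for b=0.27, and ρ=0.237 and about 138 for b=0.26.

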Blockade effect variables reflecting EO function will be derived by subtracting evoked pain responses during placebo from comparable responses during opioid blockade (separately for pre-manipulation baseline [BL] and post-manipulation). Given no theoretical rationale for expecting dose response effects with repeated dosing for placebo or naloxone conditions, we will average over the 4 pain stimuli within each of these drug conditions (separately for pre- and post-manipulation sessions) as a means of reducing random measurement error in deriving blockade effects. Blockade effects will be derived such that larger positive values reflect greater EO analgesia. To reduce number of variables, a mean value of the standardized EO function variables (blockade effects) will be derived and will be used initially in analyses (as in Bruehl et al.¹⁸). Chronic pain intensity pre- and post-manipulation will be defined as mean chronic pain ratings during the respective electronic diary sampling periods. As manipulation checks, we will determine whether degree of spontaneous EO function pre-manipulation is correlated significantly with evoked pain sensitivity and chronic pain intensity at BL. Total number of exercise minutes recorded during the post-intervention diary monitoring period (obtained in both groups) will be explored as a potential covariate for use in primary group analyses.

Primary Analyses.

Aim 1: To determine whether an aerobic exercise manipulation increases EO activity in CLBP patients, and whether these EO changes mediate manipulation-induced reductions in evoked pain responsiveness and daily CP intensity. We will conduct Group (exercise, control) x Time (BL, post-manipulation) mixed design ANOVAs to determine whether evoked pain sensitivity and CP intensity decreased significantly in the aerobic exercise group only. We will also conduct Group (exercise, control) x Time (BL, post-manipulation) mixed design ANOVAs on EO function (blockade effect variables pre- and

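### For diary back pain, random error in the EO-change mediator shifts EO-mediated effect into the direct path, so the plan's rule can call it partial or non-opioid.

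*Combined protocol and SAP*

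**What the plan says.** Section 10.0, Data Reduction and Analyses, defines EO function as the evoked pain response under naloxone minus that under placebo, separately before and after the manipulation. The mediator under Primary Analyses is the pre-to-post change in that quantity. Section 6.0 gives placebo and naloxone at separate visits about 5 days apart, so each EO-change score draws on four visits.

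The plan recognises random error. It averages the four pain stimuli within each of these drug conditions "as a means of reducing random measurement error in deriving blockade effects" and forms a mean of the standardized blockade effects. Section 6.0 also fixes the time of day and runs three threshold and three tolerance trials per task.

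The score then enters the Indirect procedure with no reliability estimate, error correction or sensitivity analysis. Mediation is tested only where the total effect of exercise is significant. The interpretation rule follows: "Significant direct and indirect paths jointly for the same outcome will indicate partial mediation". A significant direct path without a significant indirect path is taken to show non-opioid mechanisms.

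**The concern.** Averaging within a visit removes stimulus-to-stimulus error but not error common to all stimuli on that day. Four days' worth of such error remains in the difference of differences. Randomising exercise protects the effect on the mediator (a) and the total effect (c). It does not protect the mediator-to-outcome slope (b) or the direct path.

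Random error in the mediator attenuates b, and the lost part of the effect reappears as direct. The plan's rule reads that direct path at face value and does not allow for mediator error as an explanation. A larger sample does not remove the bias. At stake is the conclusion on whether an exercise effect on daily back pain runs through endogenous opioids or by another route. The plan's statement that the bootstrap needs no assumption about sampling distributions does not bear on measurement error.

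**Working it through.** **Inputs (sections 7.0 and 10.0).** n=116, and "half of the participants will be randomly assigned to undergo a 6-week supervised aerobic exercise manipulation", taken as 58 per arm. a path d=0.93. b path r=0.26 for diary pain and r=0.27 for morphine response. Two-sided 0.05.

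**The plan's own figures.** r = d/sqrt(d² + 4) = 0.93/sqrt(0.865 + 4) = 0.42, as stated. Power for the a path with 58 per arm is 0.999, so the claim that "The proposed sample size will result in a power exceeding 0.90 for testing effects of the exercise manipulation on EO function" holds. Simulated power of the bias-corrected bootstrap is 0.81 (b=0.26) and 0.84 (b=0.27) with group coded 0/1, and 0.78 and 0.805 with standardized paths. The stated 0.80 reproduces.

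**Effect of mediator error.** Let lambda be the within-group reliability of EO change, with outcome error independent of mediator error and a true direct effect c'. Then:

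- b observed = lambda × b
- indirect = lambda × a × b
- direct = c' + (1 - lambda) × a × b

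Under full mediation (c' = 0), a × b = 0.93 × 0.26 = 0.242:

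| lambda | indirect | direct | direct share |
|---|---|---|---|
| 1 | 0.242 | 0 | 0% |
| 0.7 | 0.169 | 0.073 | 30% |
| 0.5 | 0.121 | 0.121 | 50% |
| 0.3 | 0.073 | 0.169 | 70% |

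**How often the label is wrong.** Simulation with true effects held at d=0.93 and r=0.26, c' = 0, n=116, and a joint-significance test in place of the bootstrap. About 25% of trials meet the total-effect precondition at every lambda. Among those trials:

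| lambda | either label | non-opioid | partial (difference) |
|---|---|---|---|
| 1 | 10% | 6% | 4% |
| 0.7 | 22% | 13% | 9% |
| 0.5 | 36% | 26% | 10% |
| 0.3 | 54% | 47% | 7% |

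The 10% at lambda 1 is not due to measurement error. The excess over it is 12, 26 and 44 points. As a share of all trials (25% × the second column), either label occurs in about 2.5%, 5.5%, 9% and 13.5%.

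A separate simulation with the planned bootstrap and true b=0.27 gave either label in 10%, 17%, 29%, 41% and 60% of qualifying trials at lambda 1, 0.8, 0.6, 0.4 and 0.25, which is the same pattern.

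**What lambda might be.** The documents do not say. As an assumption, take session reliability R, placebo-naloxone correlation p and pre-post EO correlation q. The reliability of one blockade effect is D = (R - p)/(1 - p), and that of its change is (D - q)/(1 - q). With R=0.95, p=0.6, q=0.2: D = 0.875 and lambda = 0.84. With R=0.85, p=0.75, q=0.4: D = 0.4 and lambda = 0. The range is too wide to rule the problem in or out.

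**Outcomes that share the placebo session.** The plan does not say which drug condition supplies the evoked-pain outcome. If it is placebo, that error is also in the mediator. With a true slope of -1 and equal error in the placebo and naloxone sessions, the observed slope is -(1 + lambda)/2 and the direct share is (1 - lambda)/2, half the share above. Dividing the slope by lambda then overshoots: the corrected direct share is (lambda - 1)/(2 × lambda), about -12% at lambda 0.8 and -150% at 0.25. If the true slope is below 0.5 in size, the bias reverses sign.

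**The case against.** **The aims ask whether, not how much.** The hypotheses in section 2.0 concern a significant indirect path, decided by a 95% interval, and no proportion mediated is planned. For diary pain, mediator error pulls that test toward the null, so the test is conservative. This stands: a reader might infer that the plan could falsely claim EO mediation here, and this mechanism gives no support for that. The interpretation rule, however, also draws a conclusion from the direct path, and that part is exposed.

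**Full mediation is not assumed.** Section 10.0 describes EO function as only partly mediating the effect in the planning studies, and section 3.0 raises endocannabinoids as another mechanism. A partial label also still affirms an EO role. This stands too: that label is wrong only if the true direct effect is nil. But it is the non-opioid label, which denies an EO role, that rises most as lambda falls.

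**Error is already controlled.** The stimulus average, the composite, repeated trials and fixed time of day all raise lambda. None brings it to 1.

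**Stronger readings that do not hold.** A reader might infer that mislabelling is close to certain when lambda is low. Holding the observed effects at d=0.93 and r=0.26 while lambda falls to 0.3 gives 82%. But that implies true effects of 0.93/sqrt(0.3) = 1.70 and 0.26/sqrt(0.3) = 0.47, and the share of trials meeting the precondition rises from about 25% to 99%. It describes a much larger effect, not just a noisier mediator. A reader might also extend the 1 - lambda share to every outcome. Placebo-session evoked pain shares error with the mediator. The 25% target in Aims 2 and 3 is set against the pre-exercise placebo session, so shared error may remain there as well.

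**Conclusion.** The concern holds for diary back pain. On average a share 1 - lambda of an EO-mediated effect is moved into the direct path at any lambda below 1, and nothing in the plan corrects for it. The wrong label also needs a significant direct path, so it is a raised risk: from about 10% of qualifying trials with no error to 22%, 36% and 54% at lambda 0.7, 0.5 and 0.3.

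These rates assume full mediation, classical error independent of the outcome's error, and true effects equal to the planning values. Since the documents give no reliability, the figures are a range and not an estimate for this trial.

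**What to change.** 1. For diary pain, report direct and indirect effects corrected for mediator error (errors-in-variables or SIMEX) beside the uncorrected ones, over a stated range of lambda, for example 0.9 to 0.3. For a given lambda the corrected direct effect is c - a × b observed/lambda. In simulation with lambda known, this returned the direct share of a fully mediated effect to 0% within 0.4 points. Use within-visit stimulus variance to set the minimum error, and so the highest credible lambda. Report the lambda at which the direct path stops being significant.
2. Do not use the control arm's EO-change variance as the upper bound on error. With similar variances in the two arms it sets lambda near zero (simulated median 0.00, 5th to 95th percentile -0.22 to 0.22), and the correction is then undefined.
3. Change the interpretation rule: report a significant direct path as an effect not accounted for by measured EO change. Use the partial or non-opioid label only with the sensitivity result beside it.
4. Do not apply the simple correction to placebo-session evoked pain, or to Aim 2 and 3 outcomes whose target uses the pre-exercise placebo session, unless the shared placebo error is modelled.

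The cost is analysis code and a SAP paragraph, with no new data. The downside is wider intervals and a more cautious label.
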